## JHM IRB - eForm A – Protocol

- Use the section headings to write the JHM IRB eForm A, inserting the appropriate material in each. If a section is not applicable, leave heading in and insert N/A.
- When submitting JHM IRB eForm A (new or revised), enter the date submitted to the field at the top of JHM IRB eForm A.

\*\*\*\*\*

### 1. Abstract

- a. *Provide no more than a one page research abstract briefly stating the problem, the research hypothesis, and the importance of the research.*

Restricted nasal breathing is a common complaint among patients presenting to Otolaryngology clinics [1]. In fact, one in eight people experiences some degree of nasal obstruction, or regular difficulty breathing through the nose, which is often the result of a narrowing or collapse of the internal nasal valve [2, 3]. This condition is a daily source of discomfort that reduces productivity and quality of life [4]. Sufferers report labored breathing throughout the day, difficulty sleeping and habitual snoring, and limited stamina during sports and exercise [4].

Slight dilation of the nasal passages directly counteracts nasal obstruction and reverses symptoms in 89% of those afflicted [5]. To this end, many patients undergo functional rhinoplasty procedures to surgically widen the nasal passages [6]. However, up to 20% of patients experience unimproved or worsened symptoms postoperatively [7]. Moreover, these surgeries are invasive, requiring autologous grafts taken from the nose, ear, or ribs; and they entail a yearlong recovery period [7].

Nasal dilators such as Breathe Right strips offer a potential alternative to surgery, as they mechanically expand the nasal passages to effectively relieve obstruction. However, existing products are designed as sleep aids, and customers find them uncomfortable, difficult to use, and too visible to wear in public [8]. Although the mechanism for reversing nasal obstruction is straightforward, surgery is considered the only viable option for those who struggle to breathe during the day.

Engineers from the Johns Hopkins Biomedical Engineering Department, partnered with clinicians from the Johns Hopkins Department of Otolaryngology – Head and Neck Surgery, have developed Schnozzle, a small silicone stent to counteract nasal valve collapse and relieve restricted nasal breathing. We hypothesize that this device will improve symptoms of nasal obstruction and provide patients with a viable alternative to visible non-invasive devices or surgical management.

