### 2. Objectives (include all primary and secondary objectives)

#### *Primary objective:*

Determine the effectiveness of the Schnozzle nasal dilator compared to existing nasal dilator products and a control (unaided breathing) using objective peak nasal airflow (PNIF) measurements and the Nasal Obstruction Symptom Evaluation (NOSE) instrument.

*Secondary objective:*

Determine the comfort, inconspicuousness, usability, overall patient satisfaction, device compliance, sizing, pricing, and other patient perception of the nasal dilator products.

**3. Background** (*briefly describe pre-clinical and clinical data, current experience with procedures, drug or device, and any other relevant information to justify the research*)

Mechanical nasal obstruction is one of the most common complaints heard by otolaryngologists every day [3]. In fact, over 73% of the population experiences continually elevated inspiratory resistance as a result of obstructed nasal airflow [4]. In patients seeking treatment, the primary causes of nasal obstruction are chronic inflammation due to allergies (38%) and permanent structural abnormalities (62%) [9]. While the inflammatory causes of nasal obstruction are generally well controlled with topical and systemic pharmacotherapy, the structural impediments to airflow must be treated through mechanical alteration of these flow-limiting segments [10].

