#### **4. Study Procedures**

##### *a. Study design, including the sequence and timing of study procedures (distinguish research procedures from those that are part of routine care).*

###### **Recruitment:**

Participants will be recruited from patients presenting to Otolaryngology clinics with symptoms of nasal obstruction. The otolaryngologist in clinic will screen these patients for nasal valve collapse as they would in standard clinical practice. This involves visualizing the nasal cavity through nasal endoscopy and testing the nasal valve using Cottle maneuver (applying lateral force to the cheek to open the nasal valve) or the modified Cottle maneuver (using a cotton tip applicator to open the nasal valve from inside the nasal cavity) and evaluating for improvement in nasal obstruction symptoms. Improved nasal airflow during the maneuver suggests nasal valve collapse contributes to restricted nasal airflow.

The clinical Otolaryngologist will counsel patients with nasal valve collapse regarding the various treatment options as they would in routine clinical practice (management options include to doing nothing, using existing nasal dilator devices, or undergoing surgery). Patients will then be invited to participate in the study, which would involve a study session in which they are fitted with six nasal dilator devices, instructed in proper care and use, and report on their function and comfort. Additional participants will be recruited from patients who present to Otolaryngology clinics with symptoms unrelated to nasal breathing to serve as a control group. Participants will also be recruited via the clinicaltrials.gov website, as well as using recruitment flyers and social medial posts.

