###### **Study design:**

If a patient expresses interest in participating they will be introduced to a member of the research team to discuss the study and complete informed consent. All participation is voluntary and participants are able to withdraw from the study at any point. The study participant will be asked to complete a questionnaire, which was adapted from the previously approved survey ([IRB00122933](#)), which includes the NOSE instrument, questions regarding the patient's current treatments, and a ranking of their preferred characteristics of an ideal nasal dilator (see Appendix A).

Patients will then be asked to inhale rapidly into an airflow transducer to measure baseline peak nasal inspiratory flow (PNIF). Following the pre-test survey participants will be fitted serially with five commercially available nasal dilator products per manufacturer recommendations (Breathe Right strips, Max Air nose cones, Sleep Right dilator, Mute dilator, and Nozovent dilator), and one experimental nasal dilator designed by the research team ("Schnozzle"). In this crossover design study participants will be blinded as to which dilators are branded and which are experimental, and the order of fitting nasal dilators will be randomized. Each subject will undergo PNIF testing for all six devices.

After each fitting and use for five minutes to adjust to the device and confirm there is no immediate discomfort or irritation, participants will undergo repeat PNIF testing with each device and then will be free to go home and trial the devices on their own. Participants will be given a schedule specifying one device to trial for at least one continuous hour per day. This schedule will specify devices in a randomized order,

and participants will continue to be blinded as to which device they will be using on a particular day (Schnozzle, Breathe Right, Max Air, Sleep Right, Mute, and Nozovent). The devices will be numbered in a random fashion, for participants to be able to identify which device via the assigned number they are scheduled to use on that day. They will similarly use the device number when performing any device evaluation.

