*c. Blinding, including justification for blinding or not blinding the trial, if applicable.*

Patients will be blinded to the names of the devices tested to limit bias when they complete the surveys. They will also be blinded as to which device was designed by members of the research team.

*d. Justification of why participants will not receive routine care or will have current therapy stopped.*

The standard of care is to do nothing, use existing nasal dilator devices, or surgery. This one session comparison study of nasal dilators does not prevent patients from proceeding with the standard of care after the study session, and will familiarize them more thoroughly with available treatment options.

*e. Justification for inclusion of a placebo or non-treatment group.*

Participants will serially wear the prototype Schnozzle device and marketed nasal dilators, all of which are treatments. We will get a baseline NOSE and PNIF score from participants without any assistive devices in place, which serves as the placebo/ non-treatment arm of the study. Following the study session participants can continue to use currently marketed nasal dilators or proceed with planning surgery.

*f. Definition of treatment failure or participant removal criteria.*

Participants will be removed from the study if they experience substantial discomfort with the study devices, or if they experience any adverse events, such as epistaxis, or skin breakdown or if they would like to discontinue testing for any reason.

*g. Description of what happens to participants receiving therapy when study ends or if a participant's participation in the study ends prematurely.*

At the end of the study session participants will be able to continue using any of the marketed nasal dilator products currently on the market, and this study will not influence their ability to proceed with scheduling surgery if indicated and desired. They will not be able to continue using the Schnozzle nasal dilators at this time as it is still in early stage development and not widely produced or available.

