### c. Statistical plan including sample size justification and interim data analysis.

The purpose of this pilot study is to understand patient needs and preferences regarding nasal dilators, and to use this data to refine the design before potentially marketing the product. In this pilot study we plan to test 70 individuals with nasal valve collapse. Previous studies have demonstrated an ability to detect a statistically significant difference in PNIF with a power of 80% and an alpha of 0.05 with a sample size of 30 patients with nasal valve collapse. We aim to recruit 70 individuals, 35 patients with nasal valve collapse, 35 patients without nasal valve collapse with expected attrition of 5 patients in each cohort.[12] If we proceed to pursue statistical evaluation of the data we will use ANOVA with a  $p < 0.05$  predetermined as significant.

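### The planned ANOVA does not estimate Schnozzle against each marketed dilator, so a null result cannot support the viable-alternative half of the hypothesis, and no result can support a conclusion about surgery

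*Combined protocol and SAP*

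**What the plan says.** The hypothesis in section 1 has two halves. The first is "We hypothesize that this device will improve symptoms of nasal obstruction". The second is that the device will "provide patients with a viable alternative to visible non-invasive devices or surgical management". No criterion for a viable alternative is given there or later.

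The primary objective in section 2 is narrower: "Determine the effectiveness of the Schnozzle nasal dilator compared to existing nasal dilator products and a control (unaided breathing" is its list of comparators, judged on PNIF and NOSE. Surgery is not on it. In the recruitment text of section 4a surgery is a routine-care choice: "management options include to doing nothing, using existing nasal dilator devices, or undergoing surgery". The secondary objective and section 7b add comfort, appearance, ease of use and general favorability.

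The design is a within-person crossover of five marketed dilators and Schnozzle in randomized order: "Each subject will undergo PNIF testing for all six devices". Section 4e takes baseline NOSE and PNIF without a device, "which serves as the placebo/ non-treatment arm of the study".

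On analysis, section 7c says "If we proceed to pursue statistical evaluation of the data we will use ANOVA", with p < 0.05 as the threshold. It names no contrast, interval, margin or equivalence method.

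**The concern.** An ANOVA across conditions asks whether any of them differ. It does not say by how much Schnozzle differs from a given dilator, which is the quantity the primary objective needs. If the test is not significant, a reader may take Schnozzle to be as good as the marketed products, because no interval would be there to show how large a loss the data still allow.

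The abstract's reference to surgery raises a separate problem. It puts into the hypothesis a comparison that the objectives, procedures and outcomes do not contain. At stake is whether the conclusions drawn at the end can be traced to something the trial measured.

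**Working it through.** **1. The plan's own sample size.** Section 7c gives 30 patients with nasal valve collapse (80% power, alpha 0.05) and attrition of 5 per cohort.
- Attrition: 30 / (1 − 5/35) = 35 per cohort, and 35 + 35 = 70. This reproduces.
- The base figure of 30 cannot be reproduced, because no effect size or SD is stated. It concerns a difference in PNIF only; nothing is given for NOSE.

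**2. Assumptions for the check.** A paired contrast of Schnozzle against one dilator, n = 30 completers, two-sided 5%. Effects are in SDs of the within-person difference, since the documents give no SD.

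**3. What an interval would show.** Half-width = t(0.975, 29) / √30 = 2.045 / 5.477 = 0.373 SD. With an observed difference of exactly zero, the interval still includes a loss of 0.37 SD.

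**4. How often a real loss is missed.** Power comes from the noncentral t with 29 degrees of freedom and noncentrality d × √30.

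| True loss d (SD) | Noncentrality | Power | Non-significant |
|---|---|---|---|
| 0.25 | 1.37 | 0.263 | 74% |
| 0.35 | 1.92 | 0.458 | 54% |
| 0.50 | 2.74 | 0.754 | 25% |

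**5. Sensitivity to n.** PNIF with every device is measured at the first visit, so up to 35 patients might contribute. The half-width is then 2.032 / √35 = 0.344 SD, and the three losses are missed 70%, 48% and 18% of the time. The conclusion does not change.

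**6. What a formal similarity claim would need.** For paired non-inferiority against one dilator (one-sided 2.5%, 80% power, true difference zero), the normal approximation is n = ((1.960 + 0.842) / margin)². With the t correction, the completers needed are:

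| Margin (SD) | Completers |
|---|---|
| 0.2 | 199 |
| 0.3 | 90 |
| 0.4 | 52 |
| 0.5 | 34 |
| 0.6 | 24 |

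Thirty completers reach 80% power only for margins of about 0.53 SD or wider. The documents give no margin, so this range is illustrative.

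**7. Hypothesis against design.**

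| Part of hypothesis | Comparator in the trial | Can the data speak to it? |
|---|---|---|
| Improves symptoms | Unaided baseline (4e, 7a) | Yes, by a within-person difference |
| Alternative to visible dilators | Five marketed dilators, including the external strip (4a) | Yes by an advantage; not by a null test |
| Alternative to surgery | None | No |

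**The case against.** The strongest reply is that the protocol never defines a viable alternative as one without material loss of airflow. Its case against existing products is that they are uncomfortable, hard to use and visible, and section 9 has in mind people who now go untreated. For them, a device that beats unaided breathing and is more comfortable or discreet could be viable even with somewhat less airflow than a strip. Difference tests on PNIF, NOSE and the section 7b outcomes suit that route. This stands. A reader might infer that the trial cannot support the dilator part at all, or that a non-inferiority margin is mandatory; the documents support neither.

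It can also be said that section 7c calls this a pilot for learning preferences and refining the design, that testing is conditional, and that no passage says a null result will be read as equivalence. That stands too: the sponsor should not be charged with an inference it has not made. But a pilot is best served by estimates with intervals, which section 7c does not provide.

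Finally, the surgery wording is in the abstract and not in the objectives. That makes it a mismatch to correct, not a failure of the design.

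**Conclusion.** The concern holds in a limited form. The symptom-improvement half of the hypothesis is addressed by the unaided baseline. For the dilator half, a significant advantage on airflow, comfort or appearance could count as support, but a non-significant ANOVA could not. Under the paired, 30-completer, two-sided 5% assumption the interval spans ±0.37 SD, and true losses of 0.25 to 0.50 SD are missed 74% to 25% of the time. Whether losses of that size matter clinically cannot be judged from the documents, which give no SD or smallest important difference. For surgery, no result of this trial can support a conclusion: there are no surgical data, and section 4b limits participation to two weeks.

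**What to change.** 1. In section 7c, report the within-person differences of Schnozzle minus each marketed dilator, and Schnozzle minus unaided breathing, for PNIF and NOSE with 95% confidence intervals.
2. State there that p >= 0.05 is not evidence of similarity.
3. In section 1, limit the hypothesis to the comparators in section 2 and keep surgery as motivation only.
4. Optional: if the sponsor intends to claim that Schnozzle is as good as a marketed dilator, set and justify the largest acceptable loss before the data are opened. Say which dilators and endpoints must meet it, and check the sample size against it; 30 completers suffice only for a wide margin.

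Items 1 to 3 need no extra participants, visits or measurements. They cost a little more analysis and some redrafting, and a null ANOVA could not be cited as support for the hypothesis. Item 4 may need a larger sample.

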### 2. Objectives (include all primary and secondary objectives)

#### *Primary objective:*

Determine the effectiveness of the Schnozzle nasal dilator compared to existing nasal dilator products and a control (unaided breathing) using objective peak nasal airflow (PNIF) measurements and the Nasal Obstruction Symptom Evaluation (NOSE) instrument.

*Secondary objective:*

Determine the comfort, inconspicuousness, usability, overall patient satisfaction, device compliance, sizing, pricing, and other patient perception of the nasal dilator products.

**3. Background** (*briefly describe pre-clinical and clinical data, current experience with procedures, drug or device, and any other relevant information to justify the research*)

Mechanical nasal obstruction is one of the most common complaints heard by otolaryngologists every day [3]. In fact, over 73% of the population experiences continually elevated inspiratory resistance as a result of obstructed nasal airflow [4]. In patients seeking treatment, the primary causes of nasal obstruction are chronic inflammation due to allergies (38%) and permanent structural abnormalities (62%) [9]. While the inflammatory causes of nasal obstruction are generally well controlled with topical and systemic pharmacotherapy, the structural impediments to airflow must be treated through mechanical alteration of these flow-limiting segments [10].

The most common structural pathologies that contribute to nasal obstruction are septal deviation (54%) and internal nasal valve collapse (14%), both of which increase resistance through the internal nasal valve. The internal nasal valve is defined by the junction of the nasal septum, caudal border of the upper lateral cartilage, and head of the inferior turbinate; it contributes to two-thirds of the total nasal resistance. [3] As per Poiseuille's law, resistance increases as a factor of the radius to the fourth power. As such, small changes to the dimensions of the internal nasal valve cause an exponential change in flow. In septal-deviation, the septum- the bony and cartilaginous structure that divides the nasal cavity- is deflected, dislocated off the maxillary crest, or off-center, causing a reduction in cross-sectional area of the internal nasal valve. Valvular collapse occurs when the lateral nasal wall paradoxically moves medially on inspiration at the level of the internal valve, causing a corresponding decrease in cross-sectional area and increase in nasal resistance. The cause of which can be congenital – from weak upper lateral cartilage or lack of dilator function, develop as a result of trauma, or occur post-operatively in patients following nasal surgery [8].

There are a number of over-the-counter consumer products that attempt to relieve this mechanical nasal obstruction in an effort to avoid surgery. One of the most popular external dilators is Breathe Right, a flexible strip that is adhered to the nose and stents the lateral walls of the nose outward to prevent internal nasal valve collapse [8]. Other existing solutions take the form of nasal cones and clips that act intra-nasally to stent the collapsed nasal valve. While studies show that these products are mostly effective in increasing nasal airflow, they are typically described as uncomfortable and carry social stigma due to visibility during use, leaving their use for an extended period of time limited [11].

During the 2016 to 2017 academic year, a team of undergraduate biomedical engineering students at Johns Hopkins partnered with [name], MD, FACS, MBA, the Director of Facial Plastic and Reconstructive Surgery to design and prototype a discreet silicone nasal dilator device. A survey including the previously validated Nasal Obstruction Symptom Evaluation (NOSE) instrument and additional questions regarding nasal obstruction symptoms, management options, and characteristics desirable in a nasal dilator device has been developed and previously approved by the Johns Hopkins IRB ([IRB00122933](#)).

Based on this data and interviews with otolaryngologists experienced in diagnosing and treating nasal obstruction patients, the team developed design concepts for a mechanical nasal dilator intended to meet patient preferences for effectiveness, inconspicuousness, comfort, and usability. To date, the engineering team has conducted testing on prototypes to verify that upon compression dilators exert a dilation force consistent with the range that humans find effective in relieving nasal obstruction yet comfortable for extended periods of time. The team has assessed effectiveness of prototypes in improving nasal breathing using a model nose developed from de-identified patient images and informed by published medical research. The team also used this model with a compressed air device to confirm the stability of the dilator within the nose under extreme conditions, including sneezes and peak inspiratory flow.

The next step is to collect human data to assess Schnozzle's effectiveness in relieving nasal obstruction and source patient feedback to evaluate the success of these prototypes in meeting key design requirements of comfort, inconspicuousness, and usability. The team has conducted initial feasibility testing using the device and recording equipment to prepare and refine protocols for human subject testing.

#### **4. Study Procedures**

##### *a. Study design, including the sequence and timing of study procedures (distinguish research procedures from those that are part of routine care).*

###### **Recruitment:**

Participants will be recruited from patients presenting to Otolaryngology clinics with symptoms of nasal obstruction. The otolaryngologist in clinic will screen these patients for nasal valve collapse as they would in standard clinical practice. This involves visualizing the nasal cavity through nasal endoscopy and testing the nasal valve using Cottle maneuver (applying lateral force to the cheek to open the nasal valve) or the modified Cottle maneuver (using a cotton tip applicator to open the nasal valve from inside the nasal cavity) and evaluating for improvement in nasal obstruction symptoms. Improved nasal airflow during the maneuver suggests nasal valve collapse contributes to restricted nasal airflow.

The clinical Otolaryngologist will counsel patients with nasal valve collapse regarding the various treatment options as they would in routine clinical practice (management options include to doing nothing, using existing nasal dilator devices, or undergoing surgery). Patients will then be invited to participate in the study, which would involve a study session in which they are fitted with six nasal dilator devices, instructed in proper care and use, and report on their function and comfort. Additional participants will be recruited from patients who present to Otolaryngology clinics with symptoms unrelated to nasal breathing to serve as a control group. Participants will also be recruited via the clinicaltrials.gov website, as well as using recruitment flyers and social medial posts.

